# 3.6 Economic evaluation

An economic evaluation will be conducted from both a health care system and societal perspective. Participants will be asked to record in a diary all types and duration of hospital admissions, frequency of visits to hospital for outpatient attendances, and other visits to or from relevant health professionals (e.g. general practitioners, nurse practitioners, physiotherapists) and specify whether the main reason for the visit was fatigue. The participant will be asked to keep the diaries between the baseline and third assessment visit (approximately 28 weeks). Furthermore they will be asked to keep diaries for two weeks after the third assessment visit and two weeks before they return for the last assessment visit. National sources of unit cost data will be applied to value resource use (HRG Reference Costs, Unit Costs of Health and Social Care). The costs associated with delivery of the interventions will be estimated using records kept by therapists of the number and duration of calls per patient.

Patients will be asked to report any contacts with private practitioners, and the costs of over the counter medication/complementary therapies purchased. This also includes additional expenses related to their condition or fatigue as well as if there was an impact on paid and unpaid work.

Health-related quality of life data will be collected using the SF-12 and these data will be converted to quality of life weights using published tariffs. These data will then be used to calculate Quality Adjusted Life Years (QALYs). As the intervention may affect general well-being as well as reduce fatigue, we will also collect values for changes in well-being data using the ICECAP instrument [45] and changes in life satisfaction [46].

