Patient adherence (attendance records)	SR			х	х	Х					
Patient engagement and adherence (telephone call)	Q	3			х	Х					
Patent engagement and adherence (therapist view)	Q	2			х	Х					
Patient acceptability (Client Satisfaction Questionnaire)	Q	8				~					
Qualitative process evaluation											
Qualitative evaluation in participants (5% sample)	I										
Qualitative evaluation in therapists (all)	I										
Economic evaluation											
Health care costs from participants per diaries	D			✓	✓	√	✓				
Additional (personal) costs for participant per diaries	D			✓	✓	√	✓				
Cost associated with delivery of therapy	SR			✓	✓	√	✓				
Health related quality of life using SF-12 for calculation of QALY				✓	✓	√	✓				
Changes in well-being data using ICECAP	Q	5		✓	✓	√	✓				
Changes in life satisfaction	Q	1		~	✓	~	✓				
Optional blood sample for future ethically approved researc	 h										
1 x PAXgene RNA				✓	✓	√					
1 x PAXgene DNA				✓							
1 x serum				✓	✓	√					

**Key: B**, blood sample taken specifically for LIFT; **CRF**, part of case report form completed by research nurse during visit; **D**, separate diary for participant to keep; **I**, interviews performed after the last follow-up visit; **MR**, information extracted from medical record; **Q**, data derived from questionnaire; **S**, information obtained during pre-study invite; **SC**, Scanner; **SR**, information extracted from LIFT study records and logs; **T**, test done specifically for LIFT; **x**, outcome collection at same time frame but separate from assessment visit

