The *Personalised Exercise Programme (PEP)* is theoretically based on the premise that chronic fatigue relates to PA intolerance, supported by unhelpful illness beliefs (such as fear avoidance) and deconditioning, with a consequent increased perception of effort. PEP aims to disrupt this vicious cycle by a graded exposure behaviour therapy, which is symptom contingent, to gradually optimise patients levels of PA with view to modifying their altered perception of effort, improve their tolerance of PA, fitness and function, reverse the deconditioning and ultimately reduce the severity and impact of fatigue. Participants will receive an individually tailored graded exercise programme, initially delivered according to their physical capacity and gradually increased in duration and then intensity. The participants will receive additional information and diaries to assist

with the intervention. The times and duration of keeping the diary as well as the exchange of content will be subject to change based on the instructions of the allocated therapist. The intervention will utilise pedometers and/or heart rate monitors for goal-setting and to enhance motivation.

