# 4.3.3 Training of therapists before the study

Separate CBA and PEP training will be provided for the rheumatology nurses and physiotherapists. This will comprise an intensive 3-day group course delivered by experienced designated investigators (see delegation log in Trail Management File, TMF) supplemented with the modified therapist manuals. The course will utilise a range of methods including skills practice with specific feedback using fictitious but typical fatigued cases.

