# 4.3.4 Supervision and support of therapists during the study

Supervision will be provided by designated investigators (see delegation log in TMF) on a fortnightly basis, as required, to the rheumatology health care professionals either face to face or by telephone depending on feasibility and preference. Some of the sessions will be recorded and used in supervision to provide feedback to rheumatology health care professionals and to ensure treatment fidelity. We aim to take a 5% sample of sessions from individuals who agree to be recorded which is based on a random sample generated from an algorithm that takes into account session number, therapist, site location, patient gender. 5% of total number of sessions for those in CBA and PEP is 89 recordings, however this will be subject to participant agreeing to be recorded and treatment adherence (no sessions completed).

In addition, support will be available in cases where a rheumatology health care professional requires assistance with respect to a particular participant. In addition to direct contact option with the supervisor, we will have a notification system incorporated in the database provided and maintained by CHaRT (see 8.2). After secure log-in, the rheumatology health care professional is able to log a report with details about the issue using the participant ID number but no further identifying details included. The database will, if requested, notify the designated investigator or nominated deputy if unavailable as summarised in the delegation log in the TMF, who will provide clinical input if necessary or identify either designated supervisor to provide support if an intervention

specific issue is raised. We will aim to arrange for the rheumatology health care professional to be contacted within 24 h (based on normal working hours) regarding the issue and agreement reached on the required action to be taken and by whom.

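### Section 3.6 costs delivery of CBA and PEP from therapists' call records and makes no provision for training, supervision, devices or added materials; followed as written, it would understate the incremental cost of both active arms.

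*Protocol*

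**What the plan says.** On scope, Protocol section 3.6 states: "An economic evaluation will be conducted from both a health care system and societal perspective". For delivery cost it names one source, "records kept by therapists of the number and duration of calls per patient". Participant diaries and national unit costs cover other health care use.

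The study matrix (section 3.8) has a row headed "Cost associated with delivery of therapy". Its source code, SR, is defined in the key as "information extracted from LIFT study records and logs".

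Other sections describe resources that only the active arms use:

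- Training, given separately for CBA and PEP (section 4.3.3): "This will comprise an intensive 3-day group course delivered by experienced designated investigators".
- Supervision (section 4.3.4): "Supervision will be provided by designated investigators (see delegation log in TMF) on a fortnightly basis, as required".
- Devices, under PEP in section 4.3.1: "The intervention will utilise pedometers and/or heart rate monitors for goal-setting and to enhance motivation".
- A hands-free telephone, lent by the study team to participants who have no suitable option (section 5.3).
- Leaflets, information and diaries beyond the booklet that every participant receives (section 4.3.1).

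The SAP contains no cost analysis, and no health economics analysis plan is among the documents.

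**The concern.** None of the listed inputs is a call, so none would appear in a record of calls. Usual care uses none of them, so leaving them out does not cancel between arms: it lowers the cost of CBA and PEP and leaves the comparator unchanged.

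This bears on a stated purpose of the trial. The Summary presents central remote delivery as a way to improve cost-effectiveness, and section 1.1 names the cost of building therapist skills as a barrier to implementation. A service adopting either therapy would need trained and supervised staff. An evaluation from the health care system's perspective that prices only call time would not show that part of the bill.

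The point is separate from the face-to-face first PEP session (section 4.3.2), which a literal record of calls would also miss. It would remain even if every session were costed correctly.

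**Working it through.** **1. Inputs against the stated cost source**

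| Input | Section | Arms | Captured by call records? | Costing provision elsewhere? |
|---|---|---|---|---|
| Sessions by phone or internet | 4.3.2 | CBA, PEP | Yes | Section 3.6 |
| 3-day course | 4.3.3 | CBA, PEP | No | None found |
| Fortnightly supervision, as required | 4.3.4 | CBA, PEP | No | None found |
| Pedometers and/or heart rate monitors | 4.3.1 | PEP only | No | None found |
| Loaned telephones | 5.3 | Where needed | No | None found |
| Extra printed materials | 4.3.1 | CBA, PEP | No | None found |

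The matrix code SR does not settle the matter. The same table gives SR as the source for attendance records, which section 3.4.2 says the therapists keep. The code therefore fits the call records of section 3.6 and does not show that anything more is costed.

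**2. Direction**

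Let d be the cost per patient of the inputs that are not calls. For usual care d = 0. Costing from call records alone gives an incremental cost that is too low by d, and d is positive in each active arm.

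Cost per QALY is the incremental cost divided by the QALY difference, ΔQ. Omitting d changes the ratio by −d/ΔQ. The ratio falls if ΔQ is positive, moves the other way if ΔQ is negative, and is unstable if ΔQ is near zero.

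**3. Size**

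The documents state no delivery cost, unit cost or cost-effectiveness figure, so there is nothing to reproduce. Only an illustration in staff hours is possible.

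Inputs from the protocol: 125 participants per arm (section 5.1), so 250 in the two active arms; seven sessions of up to 45 minutes plus a booster (section 4.3.2); a 3-day course (section 4.3.3). The booster is assumed to last up to 45 minutes as well.

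- Maximum session time per patient: 8 × 0.75 h = 6.0 h.
- Both active arms: 250 × 6.0 h = 1500 h.

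*Illustration A.* Assumed, not in the documents: 6 to 20 therapists in total, 7.5-hour days, and 0.5 to 1 h of supervision per therapist per fortnight over about 18 months (39 fortnights).

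- Training: 3 × 7.5 h = 22.5 h each; × 6 to 20 = 135 to 450 h.
- Supervision: 39 × 0.5 h × 6 = 117 h, to 39 × 1 h × 20 = 780 h.
- Sum: 252 to 1230 h. Divided by 1500 h, 17% to 82%.

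*Illustration B.* Assumed, not in the documents: 4 to 15 therapists per arm, 7.5-hour days, and 26 to 52 supervisions of 0.5 to 1 h each.

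- Training per patient: 4 × 22.5/125 = 0.72 h, to 15 × 22.5/125 = 2.70 h.
- Supervision per patient: 4 × 26 × 0.5/125 = 0.42 h, to 15 × 52 × 1/125 = 6.24 h.
- Sum: 1.14 to 8.94 h. Divided by 6.0 h, 19% to 149%.

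Both illustrations count therapists' own time only, without trainer or supervisor time, devices or materials. The denominator is a ceiling, since it assumes that every participant completes every session at full length. The upper ends assume that every therapist is supervised for an hour every fortnight, although supervision is given only as required.

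**The case against.** The strongest reply is that silence is not exclusion. Section 3.6 says what delivery cost will be estimated from; it does not say that nothing else will be counted. The matrix source is broader than call records, and its delivery-cost row is ticked at week 0, whereas section 4.1 expects therapy to start 2 to 8 weeks after randomisation, so no calls exist by then. Figure 1 lists the health economic analysis as a separate publication, and the SAP appendix assigns one outcome to health economics modelling, so detail may sit in a document that was not supplied. National hourly unit costs might already include some overhead or supervision.

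It can also be said that some supervision serves the trial and not the therapy. Section 4.3.4 uses recorded sessions to check fidelity, and section 3.4.2 collects therapists' adherence ratings during supervision. One-off training needs a spreading assumption, and economics is not among the objectives in sections 2.1 and 2.2.

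Much of this stands, and it limits the claim. A reader might infer that the plan excludes these costs, that the incremental cost is certainly understated, or that cost per QALY is always pushed down. The documents do not support those readings: no text excludes the inputs, and the ratio depends on the sign of the QALY difference. The device item is also unequal across arms.

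The reply does not supply a rule. Section 4.3.1 refers to section 3.6 for the health economics analysis, section 3.6 names one basis for delivery cost, and neither the matrix row nor the SAP adds training, supervision or devices.

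**Conclusion.** The point holds in conditional form. Section 3.6 gives one basis for delivery cost, and the documents make no provision for costing the other inputs that the protocol requires in the active arms. Followed as written, the incremental cost over usual care would be understated in both arms. Training, supervision and added materials apply to both; pedometers and heart rate monitors add to PEP only; telephones depend on need.

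The amount cannot be derived from the documents. The ranges of 17% to 82% and 19% to 149% of maximum session time rest entirely on assumed therapist numbers, supervision time and day length, and they measure hours. They show that the omission could be material, not that it is of any particular size.

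The clinical effectiveness analyses are untouched. This is a change worth making to the economic evaluation, because it concerns a stated costing rule and not just absent detail.

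**What to change.** Amend section 3.6 so that intervention cost is the sum of:

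- session time;
- therapist and supervisor time from supervision logs, leaving out time spent only on trial fidelity or data collection;
- unit costs of pedometers, heart rate monitors, loaned telephones and added printed materials;
- therapist and trainer time for the 3-day course, spread over a stated number of patients or years.

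Check that the national hourly unit costs do not already include any of these, to avoid double counting. Report results with and without the one-off training cost, and vary the spreading assumption. If a separate health economics plan already covers this, a sentence in section 3.6 citing it and listing its cost components would be enough.

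The cost is a wording change plus use of training, supervision and purchase records that the study office can hold; supervision time is easiest to log as it happens. The downside is a cost-effectiveness figure less favourable to the active arms, and one assumption to state and vary.

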# 3.7 Collection of blood sample for future ethically approved research

Patients will be given the option to provide additional blood samples which will be stored in a designated freezer at the University of Aberdeen. These are a maximum of 3 tubes per visit of 1x PAXgene RNA (visit 1, 2, 3), 1x PAXgene DNA (visit 1 only), 1x serum (visit 1, 2, 3). All samples will be transferred to a designated freezer at the Imaging Centre of Excellence, Queen Elizabeth University Hospital in Glasgow and stored until analysis. Additional consent for their use in future unspecified studies will be obtained.

# 3.8 Study Matrix

	Source	Items		Prop		assess eeks]	sment
			S	0	10	28	56
Demographic data							
Date of birth, gender, marital status, employment status, level of	Q	5		✓			
education							
Characteristics of study population			-				
Overall health	Q	1		✓			
Physical activity (typical self-reported)	Q	1		✓			
Experience of fatigue for more than 3 month	Q / CRF	1	√	~			
Average level of fatigue	Q / CRF	1	v	✓			
Thyroid function test	B or MR			~			
Urea and electrolytes	B or MR		-	~			
Full blood count	B or MR			· •			
Serological status	MR			· ✓			
Erosive status	MR		-	• •			
Disease duration			_	• •			
	MR MR/CRF		-	▼ ✓	✓	✓	✓
Presence of other co-morbidities (Charlson Index)	MR/CRF		-	✓ ✓	, v	v	×
History of suicide attempts			_	▼ ✓	✓	√	✓
Inflammation (CRP/ESR)	B		_	▼ ✓	v v	▼ ✓	v √
Current pharmacological therapies	MR		_	✓ ✓	•	v	v
Blood pressure	Т		_	v			
Primary Outcome							
Chalder Fatigue Scale (Likert scoring)	Q	11		✓	$\checkmark$	✓	✓
Fatigue Severity Scale (FSS)	Q	9		✓	✓	✓	✓
Secondary Outcomes							
BRAF-MDQ (fatigue)	Q	20	-	✓	√	√	
 
✓
 

HADS (anxiety and depression)	Q	14	_	• •	· •	• •	· ·
Short Form-12	Q	14	_	· ~	· •	• •	· ·
	Q	12	_	•	· ✓	• •	· ·
Pain numerical rating scale			_	▼ ✓	v √	▼ ✓	v v
Sleep problem scale Work Productivity and Activity Impairment Questionnaire	Q	4		• •	▼ ✓	• ✓	▼ ✓
	Q Q	6 14	_	▼ ✓	v √	▼ ✓	v √
Valued Life Activities Scale (short 14 items) Global outcome	Q	14	-	v	v √	▼ ✓	v v
	Q	1			•	•	•
Additional mediator/moderator data							
Cognitions and behaviours							
Brief Illness Perception Questionnaire	Q	9		~	✓	~	~
Behavioural Response to Illness Questionnaire	Q	21		✓	~	~	✓
Clinical			-				 
Presence of fibromyalgia	CRF	8	 	~			√
Disease activity (self-reported)	CRF	2	-	· ✓	~	√	✓
Disease activity DAS28 for RA (mandatory), ASDAS, BILAG,	CRF/MR	2	-	· ✓	· ✓	· √	
 
✓
 

replaced with disease specific activity measures (non-							
mandatory)							
Physical							
Physical	-		-				· /
Physical activity profiles, over a 7 day period	T		 	√	
 
✓
 
✓
 
	✓ ✓	✓ ✓
Quantifying aerobic fitness (step) test (weight, $VO_2$ max and	Т			$\checkmark$	~	~	✓
Borg Rating of Perceived Exertion)							

	Source	Items		Prop	Proposed assessmen [weeks]						
			S	0	10	28	56				
Neuroimaging (optional)											
Multi-modal MRI scan	SC			Х		х					
Quantitative evaluation											
Patient preference	Q	2		✓							
Patient adherence (attendance records)	SR			х	х	Х					
Patient engagement and adherence (telephone call)	Q	3			х	Х					
Patent engagement and adherence (therapist view)	Q	2			х	Х					
Patient acceptability (Client Satisfaction Questionnaire)	Q	8				~					
Qualitative process evaluation											
Qualitative evaluation in participants (5% sample)	I										
Qualitative evaluation in therapists (all)	I										
Economic evaluation											
Health care costs from participants per diaries	D			✓	✓	√	✓				
Additional (personal) costs for participant per diaries	D			✓	✓	√	✓				
Cost associated with delivery of therapy	SR			✓	✓	√	✓				
Health related quality of life using SF-12 for calculation of QALY				✓	✓	√	✓				
Changes in well-being data using ICECAP	Q	5		✓	✓	√	✓				
Changes in life satisfaction	Q	1		~	✓	~	✓				
Optional blood sample for future ethically approved researc	 h										
1 x PAXgene RNA				✓	✓	√					
1 x PAXgene DNA				✓							
1 x serum				✓	✓	√					

**Key: B**, blood sample taken specifically for LIFT; **CRF**, part of case report form completed by research nurse during visit; **D**, separate diary for participant to keep; **I**, interviews performed after the last follow-up visit; **MR**, information extracted from medical record; **Q**, data derived from questionnaire; **S**, information obtained during pre-study invite; **SC**, Scanner; **SR**, information extracted from LIFT study records and logs; **T**, test done specifically for LIFT; **x**, outcome collection at same time frame but separate from assessment visit

# 4 STUDY DESIGN

The LIFT study is a multi-centre, three-arm randomised controlled trial testing usual care alone versus usual care with additional adapted CBA or PEP therapies (see 4.3).

# 4.1 Study Description

Eligible participants will be identified from about 3600 patients with IRD attending major secondary care rheumatology services in the UK (see also study flow chart under 4.2). Potential participants will be identified using local databases/clinic lists and will then be mailed or given a pre-study invite, which will include questions about fatigue (see 5.2). Potentially eligible participants will be invited to attend a baseline assessment where, if appropriate, they will be consented, the eligibility confirmed and randomised. Recruits will be randomly assigned to either a course of usual care and CBA or PEP, or usual care alone (see 6). Those in the CBA and PEP groups will receive a course of treatment involving 7 sessions delivered by telephone/ internet-based audio/video call. A booster session will be conducted 22 weeks after the start date of treatment (see 4.3). We expect that active CBA and PEP therapy will start at between 2 and 8 weeks post-randomisation,

with an average of 4 weeks after baseline. Follow-up data will be collected from all participants at 10 weeks, 28 weeks and 56 weeks after randomisation adjusted for the average delay of 4 weeks. The timeline for assessment and delivering of interventions is summarised in Figure 2 below.

[figure not shown]
[figure not shown]

Figure 2. Study time line

The primary outcome measures will be fatigue severity and impact (see 3.1). Secondary outcome measures will include those on quality of life, pain, psychological distress and work ability (see 3.2). Additional clinical, physical activity and psycho-social data will be collated to enable the identification of moderators and mediators (see 3.3 and 3.4). A subgroup of participants will be invited to take part in a nested qualitative evaluation study after they completed the follow-up (see Appendix 3). A subgroup will be invited to take part in an optional nested mechanistic observational MRI sub-study (Appendix 2). The main effectiveness analysis will be via intention-to treat including all participants (see 10).

# 4.2 Study Flowchart

# 4.3 Interventions

All participants will receive the usual care intervention and will be posted an Arthritis Research UK education booklet. Participants randomised to the active treatments will also receive either CBA or PEP. The CBA and PEP treatments are adapted from previous fatigue specific cognitive behavioural [47,48] and physical activity interventions [47] to ensure that they are suitable for a remote delivery via telephone or internet-based audio/video call and applicable the broad spectrum of IRD.

# 4.3.1 Description of interventions

*Usual care:* Due to issues of treatment access, patient education using Arthritis Research UK's information booklet for self-management of fatigue [49] represents usual care in almost all UK rheumatology centres and is freely available. The leaflet covers the major relevant topics (including fatigue validation, energy management, priorities, sleep, stress, and assertiveness) underpinned by goal-setting and self-monitoring of activity. It encourages, at several key points that the patient asks their rheumatology team for support to work through the booklet. We will not restrict what usual care may involve, but will monitor the care received for all participants as part of our health economics analysis (see 3.6).

The *Cognitive behavioural approach (CBA)* is a structured psychological intervention, which explicitly aims to replace unhelpful beliefs and behaviours with more adaptive ones. In this study, the CBA will target a number of unhelpful behavioural patterns such as 'activity avoidance' and 'all or nothing'. These can lead to negative mood states, which enhance the perception of fatigue even further. Following a brief assessment of individual patients beliefs and behaviours surrounding fatigue, the aim of the treatment is to change unhelpful beliefs and behavioural factors through the application of patient-centred strategies and behavioural activities, which are supported by written materials and regular consultations with rheumatology health care professionals. The participants will receive additional key leaflets and diaries to assist them with making changes to manage fatigue. The times and duration of keeping the diary as well as the exchange of content will be set individually for each patient following assessment and in collaboration with the allocated therapist. For example the participant may be asked to keep the rest and activity dairy for up to two weeks before a session with the therapist and they will talk about it via video call where the participant shows the diary to the therapist.

The *Personalised Exercise Programme (PEP)* is theoretically based on the premise that chronic fatigue relates to PA intolerance, supported by unhelpful illness beliefs (such as fear avoidance) and deconditioning, with a consequent increased perception of effort. PEP aims to disrupt this vicious cycle by a graded exposure behaviour therapy, which is symptom contingent, to gradually optimise patients levels of PA with view to modifying their altered perception of effort, improve their tolerance of PA, fitness and function, reverse the deconditioning and ultimately reduce the severity and impact of fatigue. Participants will receive an individually tailored graded exercise programme, initially delivered according to their physical capacity and gradually increased in duration and then intensity. The participants will receive additional information and diaries to assist

with the intervention. The times and duration of keeping the diary as well as the exchange of content will be subject to change based on the instructions of the allocated therapist. The intervention will utilise pedometers and/or heart rate monitors for goal-setting and to enhance motivation.

